This study is a prospective, randomized controlled trial that will study the postoperative clinical outcomes of levothyroxine supplementation in delayed recovery or prolonged ventilation patients post cardiac surgery.

Randomization will be performed using a computer-generated randomization sequence and allocation concealment to be maintained all through the time of procedure, by using opaque, numbered, and sealed envelopes.

The study protocol will receive ethical approval from the Research Ethical Committee/ Institutional Review Boards, Faculty of Medicine Ain Shams University.

Informed consent will be obtained from each patient before patients' allocation.

Type of the study: prospective randomized clinical trial study protocol.

Study Setting: The operating theaters and ICU of Cardiothoracic institute of Ain Shams University Hospitals.

Study period: one year.

Sample Size:

Using PASS 15 program for sample size calculation, setting power at 80% and alpha error at 0.05, it is estimated that sample size of 25 patients per group total 50 patients can detect an effect size .80 or the difference between two groups regarding different qualitative outcome measures using two-sized a z test

Study population:

Inclusion criteria:

- Age group: Adult patients from age of 45 to 70 years.

Hypothyroidism was reported to be strongly related to cardiovascular disease, respiratory complications, neurological complications, and a significant difference in ventilator weaning time [3].

- Sex: Both sexes
- Elective, urgent and emergency open heart surgeries.

Exclusion criteria:

- Patients refuse to give informed consent.
- Patient younger than 45 years old, older than 70 years old.

- Off pump patients.
- Patients known hypothyroidism on levothyroxine supplementation.
- Patients known hyperthyroidism on Carbimazole.

Sampling method:

Patients will be randomly allocated by computer generated randomization into two groups A and B:

- **Group A (Study group):** patients receiving oral supplementation of levothyroxine.
- **Group B (Control):** patients receiving Placebo drug.

Anesthetic management:

Full standard preoperative assessment for cardiac surgery will be done for all patients included in the study before planned procedures.

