Premedication will be given according to standard protocol in cardiac anesthesia. Routine monitoring included a five-lead electrocardiogram, pulse oximeter and invasive blood pressure. Anesthesia will be induced with midazolam 0.02mg/kg and fentanyl 2-5 microgram /kg and muscle relaxation were achieved cisatracurium 0.15 mg/kg intravenous. After tracheal intubation, central venous line and TEE inserted, then anesthesia will be maintained throughout the procedure with morphin20 microgram/kg /min, cisatracurium 2mg/kg/min and sevoflurane 2%. Ventilation will be adjusted to maintain end-tidal carbon dioxide in the range of 30-40 mmHg.

On ICU arrival all patients will be subjected to standardized management as per institutional protocols. Patients who show signs of delayed recovery defined as either prolonged ventilation for 48 hours or delayed conscious level recovery for 48 hours despite exclusion of muscle relaxants and/or sedative drugs. Those patients will undergo CT brain, CT chest and neurological examination to exclude structural damage as per institutional protocols. Also, metabolic profile screening including full kidney function, full liver function, electrolyte and thyroid profile (TSH, free T3, free T4) to exclude correctable metabolic abnormalities.

Patients then divided into two groups: group A will receive levothyroxine via Ryle, dose of 25 to 50 ug/ day according to BMI, while group B will receive placebo in form of inert starch tablet.

Daily assessment of conscious level according to Glasgow Coma Scale (GCS) and spontaneous breathing trial by ICU consultant till ICU discharge.

Assessment of thyroid profile (free T3, free T4, TSH) before hospital discharge.

Endpoints of the study:

Primary end point:

1. Improvement of Glasgow coma scale and spontaneous breathing trial before ICU discharge.

Secondary end points:

1. Total ventilation time.
2. Total ICU stay.
3. Total hospital stay.
4. Total amount of inotropic support.
5. Improvement of cardiac function by echocardiography.

Ethical considerations:

The study protocol will receive ethical approval from the Research Ethical Committee, Faculty of Medicine Ain Shams University.

Informed consent will be obtained from each patient before patients' allocation.

Sample Size Calculation

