Using PASS 15.0 (NCSS LLC), detecting an effect size of 0.80 in GCS change ($\alpha = 0.05$, power = 80%) required 25 patients per arm. To ensure adequate power for secondary endpoints and allow for dropouts, we enrolled 35 patients per group (total $n = 70$).

Statistical Analysis

Analyses adhered to the intention-to-treat principle. Continuous variables are reported as mean \pm SD or median (IQR) and compared using Student's t-test or Mann-Whitney U test, as appropriate. Categorical variables are expressed as counts (%) and compared by χ^2 or Fisher's exact test.

- **Primary analysis:** Linear mixed-effects regression modeled GCS trajectories over time, with group, time, and their interaction as fixed effects and patient as a random effect.
- **Time-to-event outcomes:** Kaplan-Meier curves and Cox proportional hazards models yielded hazard ratios (HRs) and 95% confidence intervals (CIs).
- **Mediation:** The Sobel test quantified the proportion of EF preservation attributable to changes in free T3.

- **Sensitivity and subgroup analyses:** Inverse probability weighting assessed robustness; prespecified subgroups included diabetes status and CPB duration > 200 minutes.

All tests were two-tailed with $\alpha < 0.05$. Statistical analyses were performed using R v4.3.1 with the lme4, lavaan, and survminer packages.

4. REFERENCES (Maximum 20 references)

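### If levothyroxine shifts free T3, the mediation analysis can credit free T3 with EF preservation it did not cause, because the free T3-to-EF path is neither randomised nor adjusted

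*Combined protocol and SAP*

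**What the plan says.** The Mediation bullet under Statistical Analysis reads: "The Sobel test quantified the proportion of EF preservation attributable to changes in free T3". It gives no path equations, covariates or statement that unmeasured common causes are assumed absent.

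The next bullet names inverse probability weighting as a robustness check. It does not say which covariates enter the weights or which analysis is weighted, and it does not link the weighting to the mediation. The same bullet states that "prespecified subgroups included diabetes status and CPB duration > 200 minutes".

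Only the treatment arm is randomised (Methodology, Sampling method). Free T3 is measured before allocation, in the work-up of delayed recovery: "electrolyte and thyroid profile (TSH, free T3, free T4) to exclude correctable metabolic abnormalities". It is measured again before hospital discharge. Cardiac function by echocardiography is the fifth secondary endpoint, with no time point given. Mediation is not among the listed endpoints.

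On size and error level, "we enrolled 35 patients per group". The Statistical Analysis section makes all tests two-tailed at 5%.

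**The concern.** The mediated effect is the product of two paths. Path a, from arm to free T3 change, is a randomised comparison. Path b, from free T3 change to EF within arm, compares patients who happened to have different free T3 changes. It is observational, and neither allocation concealment nor intention-to-treat protects it.

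Shared causes are plausible here. The trial takes elective, urgent and emergency open-heart surgery, and it studies patients with delayed recovery at 48 hours. Illness severity or bypass burden could affect both free T3 and EF. The plan considers bypass duration and diabetes important enough for subgroups, yet names neither in the mediation. The documents do not quantify any such confounding.

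At stake is the plan's only mechanistic statement. A reported share of EF benefit acting through free T3 could reflect who was sicker rather than what the hormone did.

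**Working it through.** **The plan's own figure.** The documents give no figure for the mediation. The nearest is the sample size: "detecting an effect size of 0.80 in GCS change" at two-sided 5% and 80% power "required 25 patients per arm". Check: n = 2(1.960 + 0.842)² / 0.80² = 2 × 7.85 / 0.64 = 24.5, so 25 per arm. The t-test version gives 25.5, so 26. The figure reproduces, but it concerns GCS and says nothing about free T3 or EF.

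**Inputs.** From the documents: 35 per arm and two-sided 5%. Assumed, because the documents do not give them:
- a, the shift in free T3 change, in SD units;
- ρ, the within-arm correlation between free T3 change and EF induced by a shared cause;
- c, a purely direct treatment effect on EF, in SD units.

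The true effect of free T3 on EF is set to 0 throughout.

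**Model.** Two ordinary least-squares fits: free T3 change on arm (gives a), and EF on arm and free T3 change (gives b). The statistic is z = ab / √(a²·SE_b² + b²·SE_a²), rejecting if |z| > 1.96.

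**Expected size by hand.** With unit residual variances, confounding makes b estimate ρ, so the false indirect effect is aρ and the false proportion is aρ/c. For a = 0.8, c = 0.8:
- ρ = 0.3: 0.8 × 0.3 = 0.24 SD; 0.24 / 0.8 = 30%.
- ρ = 0.2: 0.8 × 0.2 = 0.16 SD; 0.16 / 0.8 = 20%.

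For z at a = 0.8, ρ = 0.3: SE_a² ≈ 2/35 = 0.0571 and SE_b² ≈ (1 − 0.09)/68 = 0.0134. Then z ≈ 0.24 / √(0.64 × 0.0134 + 0.09 × 0.0571) = 0.24 / 0.117 = 2.05. This is just above 1.96, so rejection in about half of trials is expected.

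**Simulation with a purely direct effect, c = 0.8** (35 per arm; true proportion mediated 0):

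| a (SD) | ρ | Sobel rejects | Median proportion mediated |
|---|---|---|---|
| 0 | 0.3 | 0.7% | 0% |
| 0 | 0.5 | 3.3% | 0% |
| 0.8 | 0.2 | about 19% | about 19% |
| 0.8 | 0.3 | about 47% | about 29% |
| 0.8 | 0.5 | 85% | 49% |
| 1.2 | 0.3 | 67% | 44% |
| 1.2 | 0.5 | 99% | 74% |

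The rejection rate does not depend on c, because b is estimated given arm; c only changes the denominator of the proportion.

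**Mild and opposite cases.** At a = 0.2, rejection is 0.7%, 3.2% and 6.2% for ρ = 0.2, 0.3 and 0.4. At a = 0.8, ρ = 0.1 it is 4.7%. At a = 0.8, ρ = −0.3 every rejection is in the negative direction, so the proportion is biased downward.

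**Effect of adjustment.** If covariates in both equations capture half or 80% of the shared cause, rejection at a = 0.8, ρ = 0.3 falls from about 47% to about 18% or 5–6%. If they capture all of it, rejection at a = 0.8, ρ = 0.5 falls from 86% to 3%. How much the available covariates would capture is unknown.

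**The case against.** The case on the other side has real force.

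- **The null.** A reader might infer that the Sobel test merely tests whether free T3 change and EF are associated. It does not; its null is a*b = 0. With a = 0 and ρ = 0.3, the test of b alone rejects 74% of the time and Sobel 0.6%.
- **A shared cause is not enough.** A reader might also infer that confounding by itself makes the test report mediation. The arm must shift free T3 too. At a = 0, rejection stayed at or below 3.6% for ρ up to 0.5. This limits the point but does not remove it, since a mediation claim would be made only when free T3 moved.
- **No EF effect to apportion.** If treatment has no effect on EF, high Sobel rejection rates do not measure how often a share of EF preservation would be wrongly reported. Requiring both a significant EF benefit and a positive Sobel result brings the rate below 3% over the shifts and correlations examined. The plan states no such gate, but the table above uses a real direct effect for this reason.
- **Assumed inputs.** Neither a nor ρ is in the documents, and the 0.80 there is a GCS effect size. The mediator is a change score, so sicker patients could start lower and rebound more, making ρ negative. This stands; the size is illustrative and its direction is not settled.
- **Inverse probability weighting.** The plan does name it, so it would be wrong to say there is no robustness analysis at all. Without covariates, a target or a link to the mediation, it cannot be counted as covering path b.
- **Generality.** The same caveat applies to any single-mediator analysis in a randomised trial, and this one is not a listed endpoint. That argues for low priority, not for leaving the causal wording in place.

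**Conclusion.** The point holds in a limited form. The plan draws a causal share from a product of paths, one of which is unrandomised and has no stated adjustment. If levothyroxine shifts free T3 appreciably and a shared cause links free T3 change to EF, the analysis can show a significant indirect effect and a sizeable proportion mediated when the true share is 0.

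Under the central assumptions (shift 0.8 SD, correlation 0.3, direct effect 0.8 SD, 35 per arm) that means about 47% rejection and a median share of about 29%; at correlation 0.2, about 19% and 19%. With a small shift or weak correlation the error rate stays near or below about 6%. A negative correlation biases the share the other way.

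The documents do not support a statement that the mediation result will be false, or that its error rate has any particular value. The primary GCS analysis is unaffected. This is a cheap improvement to a minor, non-endpoint analysis.

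**What to change.** 1. Write out both path equations (free T3 change on arm; EF on arm and free T3 change) and include the same pre-allocation covariates in each: baseline free T3, bypass duration in minutes, diabetes, urgency of surgery, and baseline EF where recorded.
2. Report the residual free T3–EF correlation at which the indirect effect becomes zero. This is needed because the listed covariates may not capture illness severity.
3. Replace *attributable to* with *statistically associated with, assuming no unmeasured common cause of free T3 change and EF*, and label the analysis exploratory.
4. State whether the inverse probability weighting applies to the mediation and, if so, with which covariates.

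Cost: SAP wording and a few model lines in R, with no new patients or measurements. With three urgency categories the covariates use at most 1 + 1 + 1 + 2 + 1 = 6 degrees of freedom per equation, out of 70 patients. The mechanistic claim becomes weaker.
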